Arms 1 & 2 (Intervention). Twenty-four women will be randomized to the 2 arms of the intervention involving written emotional disclosure in English or Spanish. During the 4 writing days, participants will be asked to write about the most traumatic or upsetting experiences of their entire life. In their writing, they will be asked to “really let go” and explore their “very deepest emotions and thoughts.” Subjects will be told that it is best to write about a major trauma and encouraged to write about the same experience on all 4 days. However, they will also be told it is okay if they write about current conflicts. Subjects will be encouraged to write about traumas or conflicts they have not discussed in great detail with others. They will be told to write continuously for 20 min. These instructions were developed by [name] and based upon those used in previous studies (70, 71), that were adopted along with a writing probe to assess the effect of WED on post-traumatic, depressive and disease related outcomes amongst HIV+ women (60). Scripts and instructions will be delivered exclusively in Spanish for the S-WED group and exclusively in English for the E-WED groups. When the 20-min writing session is complete, subjects will be asked to write for an additional 10 min and given the following instructions (processing probes) for each session, respectively. Session 1: How you have tried to understand and make sense of the traumatic experience(s)?; Session 2: How does the traumatic experience affect your feelings about yourself, your self-worth, and your self-esteem?; Session 3: How does the traumatic experience affect your ability to solve problems, to meet future challenges, or to deal with day-to-day stress?; and Session 4: How have you tried to understand the trauma and make sense of it?

Arm 3 (Daily event writing). Twelve women will be randomly assigned to the daily event writing condition will be asked to write a description about what they did “yesterday from the time [they] got up until the time [they] went to bed” for 20 min continuously. We will counterbalance the language used by these women to journal about their daily events. They will be told to “avoid writing about [their] emotions or opinions” but to try to be as “accurate and objective as possible.” The 20-min writing period will be followed by 10 more min of describing in writing what they

IRB Study Number: 20190760

Version: 10 Date: 06/06/2022

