- (3) Based on the suicide assessment outcome and consultation with the postdoctoral fellow and/or supervisor, determine whether the participant is at low, moderate, severe, or extreme risk of suicide.
- (4) Decide on next steps depending on risk level (in consultation with postdoctoral clinical fellow, who will then consult with primary or backup supervisor as indicated in the Suicide Risk Assessment Packet).

Participants will also be monitored for elevated levels of psychological distress throughout the course of the study. Specifically, participants will be queried regarding their distress levels before and after each session using the SUDS as well as the POMS. These measures will be scored immediately following each session. If levels of distress are elevated, we will go over ways of reducing distress via coping and stress management strategies in conjunction with the distress packet:

- (1) Things I can do to help cope (e.g., exercise, playing music, relaxation exercises, hot shower, journaling, etc.).
- (2) People I can contact to distract and/or support me (e.g., friend, therapist, mentor, relative, religious leader, etc.)
- (3) Three positive things I can focus on right now (e.g., something good in my life, something positive that happened, a beautiful sunset, people who care about me, an inspirational thought, a nice memory, etc.).

Access to participant records will be limited to the study staff. All records are kept using a study ID number. Participant number and name will appear together only on one form. That form will be kept in a separate locked cabinet to which only the lead Study Coordinator will have access. All other forms will contain only study ID number. Participant name or other identifiable information will not appear when we present this study or publish its results. Any staff with access to identifying information will be required to sign a confidentiality pledge, which prevents them from sharing any personal information with anyone else. The signed informed/consent form will stay with PI. Only coded information will be shared with researchers and other doctors that are part of this study.

Participants will be informed that they have the right to have their data (specimen, neuroimaging, psychometric) destroyed at any time following completion of the study.

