In the event of any untoward events or conditions that endanger the participant's health, safety, and rights, suspension of the research will occur barring a full report of the event to the University of Miami IRB. In the case of an adverse event, i.e., unanticipated problem associated with the study, a report will be made indicating: 1) type related to psychological/mental or physical events; 2) severity related to the degree to which psychiatric or medical intervention is required; 3) scope of the event related to the impact it had on the participant's ability to complete all study requirements; 4) consequence of the overall event; and 5) if applicable, frequency of the problem. This report will be forwarded to the HRSO office within 10 days of the study team becoming aware of the adverse event. A section of our psychosocial surveys do address suicidal ideation. In order to minimize risk to the participant we have added language to the confidentiality section regarding our intention to intervene if suicidal ideation is derived from survey items. Screening data from the MINI psychiatric interview will be reviewed to determine if it meets criteria for moderate to high potential suicide risk, based upon recommended guidelines. In addition, high suicide risk may be assessed by an individual item on the Beck's Depression Inventory-2. The study PI is qualified to complete the evaluation. If the screens are positive and the participant is believed to be at risk, study team members will work with the participant contact their doctor, a trusted family member, or a therapist to discuss their thought. In more critical situations the study staff may work with the individual on a plan that might include getting them safely to a hospital environment. This data will not be reported as a part of the analysis.

IRB Study Number: 20190760

Version: 10 Date: 06/06/2022

15) Provisions to Protect Subjects

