Additionally, there will be a distress management plan. In the event a participant becomes distressed due to study procedures, the coordinator will ask the participant if he or she would like to withdraw from the study, and the research personnel will consult and refer the participant to the appropriate services if necessary. If necessary, participants will be referred to local service providers where they can receive treatment. Participants may feel uncomfortable about some of the questions that they are being asked about their traumatic experience, but will do so under the supervision of a trained trauma therapist. Finally, participants will be debriefed after each trauma recall exposure as it is important that those affected by traumatic events or their recall be provided practical, pragmatic psychological support and information about possible reactions and about how to help themselves access support from around them. Furthermore, participants will be contacted by the study coordinator within 24-72 hours of their writing session to ensure they are not experiencing elevated levels of distress in response to the writing probe.

We will take every precaution to ensure the participant does not experience a burdensome amount of distress associated with fMRI paradigm. Prior to the actual

IRB Study Number: 20190760

Version: 10 Date: 06/06/2022

scan the participants will go through a simulation in a “mock scanner” where they will be introduced to the task and the ambient sounds (MRI noise) they will be hearing during the actual scan. During the actual scan participants will have constant interaction with the researcher and MRI technician. Participants will be provided with an emergency squeeze ball that they may engage at any time to stop the procedure. Furthermore, we will continuously monitor heart rate, respiratory rate, and blood pressure so that we can ascertain whether the participant is experiencing excessive psychophysiological distress. We will take all available precautions to make the participant comfortable, e.g., allow time for acclimation, practice using a mock scanner, provision of blankets and ear protection, etc.).

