We will make sure that every participant feels comfortable to let us know if they feel any discomfort, and most importantly, to let us know if they want to stop the study. Participants will be informed that the best way to minimize these events is to not clasp one’s hands together and not cross one’s legs during scanning. Should discomfort arise, participants may stop the scan at any time and for any reason. We will stop the study as soon as a participant communicates to us that he/she wants to stop the study. Subjects will be monitored throughout the entire experiment. They are reminded that the experimenters can see and hear them at all times to address any problems that they are having. We also interview each subject who completes our MRI studies following the study. Subjects will be reminded before the experiment that their participation is completely voluntary and they may stop the experiment at any time and for any reason without penalty. If, in the opinion of the study staff, PI, subject, or participant’s family, the procedures or study participation will be discontinued if they are adversely affecting the subject’s emotional well-being. This may happen even if the participant does not request stopping. At this point, subjects will be interviewed and staff will determine what additional steps should be taken.

With regards to incidental findings resulting from the fMRI scan, the imaging facility is a research facility, not a medical facility. The MRI scans obtained at the imaging facility are research scans, to be used for scientific purposes. The scientists who review the scans are not physicians and they have no competence in evaluating the scans for medical or therapeutic purposes. These scans are not meant to provide clinical information although all research scans will be read by a radiologist. If any results of clinical significance are found, we will communicate this information to the participant. This consultation will not result in an additional charge to the subject in question. Based on the radiologist's assessment, we may recommend that participants seek advice from your primary physician or a specialist. The University of Miami will not be responsible for any costs relating to standard medical care. Participants will be responsible for such costs, in such an event.

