Cox neuroscience Annex is a The 1200 square foot MRI facility is housed on the first floor of the three-floor, 37,700 square foot Neuroscience building adjacent to the Cox Science Building on the University of Miami Coral Gables Campus. The facility encompasses a MR scanner suite with associated reception and waiting areas, dressing rooms and a MR simulator/mock scanner suite. The Neuroimaging Suite has a state-of-the-art GE®MR750 3.0T MR scanner and 32-channel head coil capable of performing structural and functional scans in human subjects. The MR suite is equipped to deliver visual, auditory, and tactile stimuli. In addition, behavioral and physiological responses and eye movements can be recorded. The remaining 11,000 square feet on the first floor of the building includes shared space including a large

IRB Study Number: 20190760

Version: 10 Date: 06/06/2022

conference/multipurpose room, kitchen, restrooms, behavioral testing rooms, a central server room, a phlebotomy room, and an assay lab. Equipment includes: Psychology Software Tools, Inc. Hyperion MRI Digital Projection System, PST-100984; Current Designs 932 fORP Response Devices (4-button diamond, 4-button inline, 5-button Pyka, Trackball2); Biopac Physiological Recording (Heart rate, respiration, skin conductance response, electrocardiography, electromyography, blood pressure); Avotec, Inc. Silent Scan SS-3300 Hearing Protection, Communication and Music System; Resonance Technology Eye-tracking (used with 8-ch head coil); Midwest Composite Technologies MRI System Simulator; Psychology Software Tools, Inc. Motrak Head Motion Tracking System, PST-100722; and Video camera monitoring.

All research staff will have to participate in a regularly scheduled MRI safety training session. This session will ensure that all research staff are aware of the potential dangers of MRI testing and assure the safety of the participant at all times.

23) Prior Approvals

Upon approval by UM IRB, the project will be submitted for review by an independent committee at the Cox Neuroimaging Facility. This committee will determine whether the protocol may need to be further modified in order to ensure patient safety.

24) Local Number of Subjects

The total number of subjects to be accrued locally will be 36.

25) Confidentiality

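### Responses to participant distress are not reconciled, women who stop writing have no stated route to Session 6, and no by-arm summary of the expected harm is planned

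*Combined protocol and SAP*

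**What the plan says.** Distress is dealt with in several places:

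- **Section 14**, safety monitoring: SUDS and POMS are taken before and after each session. "If levels of distress are elevated, we will go over ways of reducing distress via coping and stress management strategies".
- **Section 15**, opening paragraph: a bilingual trauma therapist reviews the scores and checks in briefly with each participant.
- **Section 15**, distress management plan: "the coordinator will ask the participant if he or she would like to withdraw from the study", with consultation and referral where needed.
- **Section 15**, scanning text, repeated under MRI Risks in Section 17: "the procedures or study participation will be discontinued if they are adversely affecting" the participant's emotional state. Staff, the PI, the participant or her family may form that opinion, and she need not have asked to stop.
- **Section 16**: the only anticipated withdrawal without consent is undisclosed metal found at the MRI facility. Participants may decline particular assessments. Those who withdraw early may have their data destroyed.

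On harms, the Adverse Event text in Section 14 equates an adverse event with an unanticipated problem and sends each report singly to the human-subjects office. After describing suicide-risk screening from the MINI and a BDI-II item, it states: "This data will not be reported as a part of the analysis".

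On numbers, "The total number of subjects to be accrued locally will be 36". "Twenty-four women will be randomized to the 2 arms of the intervention involving written emotional disclosure in English or Spanish", and "Twelve women will be randomly assigned to the daily event writing condition".

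**The concern.** The distress provisions do not say which applies when, or whether one follows another. Their common gap matters most for the statistics: stopping the writing is never separated from leaving the study. A woman who reacts badly, is offered withdrawal and accepts has no stated route to Session 6. If such women would have had poorer IES-R or Hopkins results, those who remain look better than the arm as randomised, and a comparison with daily-event writing is tilted towards the trauma writing.

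The harm that the protocol itself anticipates also has no planned place in the results. Section 17 attributes the study's risk to recalling severe trauma, yet expected distress can fall outside the adverse-event definition and the suicide-risk data are kept out of the analysis.

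**Working it through.** **1. Sample size.** 24 + 12 = 36, which agrees with Section 24. The split of the 24 is not stated; 12 per trauma arm is assumed below. No alpha, power, SD or dropout allowance is given, so no planned operating characteristic can be reproduced.

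**2. Can the distress provisions be placed in one sequence?** Section 14 is triggered by elevated scores (no threshold given). The Section 15 offer is triggered by distress from study procedures. The Section 15 and 17 discontinuation is triggered by an adverse effect on emotional state. The triggers overlap and no order is stated. Section 16, with metal as its only anticipated non-consented withdrawal, does not match discontinuation without a request in Sections 15 and 17.

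**3. What is lost if Session 6 is lost?** Table 1 schedules the IES-R and Hopkins task at T1 and T6 only. A woman who misses T6 has no post-intervention value on either primary outcome.

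**4. What differs by arm after randomisation?** Section 9 randomises at the second visit, after baseline. Up to Session 6 the scheduled difference is the writing: trauma in two arms, neutral daily events in the third (Section 8). More distress-related stopping in the trauma arms is a reasonable inference from this. No rate by arm is given.

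**5. Does the analysis deal with it?** Section 12 names linear mixed models, with no analysis population or missing-data rule. Such a model uses a leaver's baseline and is valid if loss depends only on observed data. It does not remove bias when loss depends on the unseen Session 6 result, and destroyed data cannot enter it.

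**6. Illustrative size.** Let C and L be the mean improvement of completers and leavers, and p the proportion leaving. The full-arm mean is (1 − p)C + pL, so the completers' mean exceeds it by p(C − L). The gap C − L is assumed: 15 IES-R points, and half that, on a scale with maximum 22 × 4 = 88.

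| p | gap 7.5 | gap 15 |
|---|---|---|
| 5% | 0.05 × 7.5 = 0.375 | 0.05 × 15 = 0.75 |
| 1/12 | 0.625 | 1.25 |
| 2/12 | 1.25 | 2.5 |
| 3/12 | 1.875 | 3.75 |

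The 5% row borrows the Section 15 remark that fewer than 5% need extra counselling. That is not a withdrawal rate.

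A simulation with 12 per arm, no true effect, exactly the worst responders lost from one arm, and a completers-only t-test at two-sided 5% gave:

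| Lost of 12 | Shift in arm mean (SD) | Rejection rate | Favouring that arm |
|---|---|---|---|
| 0 | 0.00 | 4.9% | 2.5% |
| 1 | 0.15 | 7.3% | 6.0% |
| 2 | 0.28 | 11.3% | 10.6% |
| 3 | 0.39 | 16.5% | 16.2% |

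This is an extreme case, and it is not the planned model.

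**7. Suicide-risk data.** Table 1 places the MINI at T1 only, before randomisation, so it cannot show harm by arm. The BDI is at T1 and T6, so its suicide item at T6 is post-randomisation and falls under the exclusion. SUDS and POMS (every session) and the BDI and IES-R totals are not excluded.

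**8. What could a harms table show?** With 0 events in 12, the one-sided 95% upper limit is 1 − 0.05^(1/12) = 22%; with 0 in 24 it is 1 − 0.05^(1/24) = 12%. Such a table can only be descriptive.

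**The case against.** The responses can be read as cumulative: support, check-in, offer and referral, then discontinuation. The distress plan in Section 15 is introduced as an addition to what precedes it, and the discontinuation rule sits in scanning text. On that reading the main defect is a missing order rather than a contradiction. This stands in part, but the wording of the discontinuation rule reaches study participation as a whole, and its mismatch with Section 16 remains.

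Four stronger readings are tempting, and the documents do not support them.

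- **That two of the rules end participation.** The coordinator only asks. The discontinuation rule can end participation, but it also names stopping the procedures alone.
- **That leaving the study is the only exit.** Section 16 lets participants decline particular assessments and stay in. What is missing is a statement that Session 6 follows when writing stops.
- **That loss will occur in the trauma arms and hardly at all in control.** Section 10 has control women hear personal trauma recordings in the scanner too, and at Session 6 the scan comes before the test battery. They therefore also meet a possible trigger before the primary outcomes are taken.
- **That harms go unreported.** Adverse events are reported individually, and several distress measures are collected and open to analysis. What is absent is a plan to summarise them by arm.

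It is also fair that similar loss in both trauma arms would largely cancel in the Spanish-versus-English contrast. The exposure is mainly in trauma writing versus control.

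**Conclusion.** The point holds as a gap in the plan. The distress provisions in Sections 14, 15 and 17 are not reconciled with one another or with Section 16. No text keeps a woman who stops writing in follow-up to the only post-intervention primary assessment. No by-arm summary of the anticipated harm is planned, and the suicide-risk data, including the post-randomisation BDI-II item, are expressly kept out of the analysis.

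Bias in favour of trauma writing is plausible but not shown. It requires that distress leads to leaving, that it does so more often in the trauma arms, and that leavers would have done worse at Session 6. The documents establish none of these. The IES-R and simulation figures show only that one or two such losses could matter with about 12 women per arm. They describe a completers' comparison under assumed inputs and do not predict the result of the mixed model. The change is worth making because it is cheap and the loss cannot be repaired afterwards.

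**What to change.** (a) The sponsor should reconcile the distress provisions in Sections 14, 15 and 17 with each other and with Section 16. The clinical rule is the investigator's to set.

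(b) Define stopping the writing sessions separately from withdrawing from the study. Women who stop writing and still consent are invited to Session 6 for at least the IES-R and Hopkins task, keep their Section 16 rights to decline any part or have data destroyed, and are analysed in their randomised arm. Count reasons for stopping, and any data destruction, by arm.

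(c) Replace the closing sentence of the Adverse Event text in Section 14 with a de-identified descriptive table by arm covering post-randomisation suicide-risk escalations, distress scores, referrals, adverse events, stops of writing and withdrawals. Report distress as scores, since no threshold for elevated distress is defined.

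The cost is protocol wording, a few Session 6 visits (already in the schedule) for women who stopped writing, and simple logging of referrals and stops, which the documents do not show is being done now.

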have done “today from the time [they] woke in the morning.” These instructions will be modified slightly for three subsequent writing sessions to reflect descriptions of what they did on different days or what they planned to do on future days.

9) Study Timeline

The timeline will begin once the participant has signed the informed consent. Upon acquiring informed consent data will be collected during 6 separate time points. After the baseline session (1a & 1b) participants returned for the second study visit where they will be randomized to either the English trauma-writing intervention, the Spanish trauma-writing intervention or the daily-event-writing control. Experimental and control participants will be asked to visit their study based on their randomized assignment for a total of four occasions over a 4-week period so that they can engage in an online expressive writing exercise for 30 min. After each writing session, the writings will be submitted online to the researcher staff. All writings will be de-identified before being stored on secured UM servers and analyzed by study staff. Questionnaires, interviews, blood draws, neurocognitive assessments and neuroimaging data collected during session 1 were again administered 1 months after the end of each participant’s writing intervention. Upon completion of the session 6 participants involvement with the current study be complete and there will be no other study requirements.

10) Data Collection

Blood Assays. Approximately 50 ml of blood will be drawn from all participants, once at the first time point and up to 2 times (before and after neuroimaging session) at all subsequent time points. HIV-1 viral load and CD4 count will be recorded from each participant based upon the last labs drawn. Because menstrual cycle phase influence PTSD symptom presentation profile and psychophysiology (72, 73) data collection for all pre-menopause women will take place in the luteal phase and blood banked for ovarian steroid hormones, (e.g., estradiol). A salivary ACTH kit will be used to measure HPA-axis activity pre-scan and again following trauma recall. Peripheral GC sensitivity was tested by measuring in-vitro stimulated production of interleukin-6 (IL-6) in whole blood before and after cortisol vs. placebo application. Salivary cortisol will be analyzed using an Elisa plate reader at the Diabetes Research Institute under the supervision of [name].

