
Cardio-autonomic Function. In addition to understanding vascular mechanisms this research is also based upon autonomic mechanisms. Parasympathetic and sympathetic function will indexed by heart rate variability (HRV). Because of the variation in measure and interpretation of HRV we will use methodology recommended by the Task Force of the European Society of Cardiology for both

IRB Study Number: 20190760

Version: 10 Date: 06/06/2022

time and frequency domain (88). These values will be derived by in-house software made available by Bipoac™ that record and transform HRV from the R-R intervals gathered from spontaneously measured heart rate within 2 to 5 minute intervals. Overall 5 domains of HRV will be measured in the study (see Table 1) indexing relative levels of sympathetic and parasympathetic cardiac input.

Neuroimaging Protocol. Functional and structural brain scans will be performed on a GE MR750 3.0-Tesla scanner during a 30-minute session. The protocol will consist of 1. Resting-state functional scan (5 minutes), 2. Functional scan during a verbal learning and memory task (12 minutes), 3. Structural/anatomical MRI scan (5 minutes) 4. Trauma recall (5-minutes).

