Trauma Recall in fMRI. The 5 minutes allocated to trauma recall within the scanner will be facilitated by an “autobiographical script-driven imagery” protocol adapted for the fMRI environment (89, 90). During the protocol participants will listen to recordings of personal trauma episodes (recorded during session 1a) and will be asked to focus on the evoked mental images and feelings. Recordings and prompts to recall the trauma in primary (Spanish) or secondary (English) language will be matched to the intervention group to which the participant was randomized. During the protocol four 40-second scripts will be constructed for each subject from personal interviews, describing either aversive (e.g., sexual or childhood trauma) or neutral events. Two traumatic and two neutral conditions will be selected and played during scanning counter-balancing for valence. Participants will be instructed to focus on scripts and maintain the evoked images and states. Participants will also rate their evoked emotional states after each scan using a modified version of the Positive and Negative Affect Schedule (PANAS) (91). "Participants will be scanned at baseline and after the 4 WED sessions writing about trauma in English or Spanish or the 4 sessions of writing about daily activities (for the control group). Three salivary cortisol samples will be collected. The first sample will be collected just prior to beginning the 30-minute scan. The second and third collections being 5 minutes and 10 minutes after conclusion of the scan. Salivary ACTH will be assayed using a radioimmunoassay kit and analyzed at the DRI.

[figure not shown]

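### The 24-72 hour distress contact is stated for writing sessions only, so none is stated after the Session 6 scan visit, which includes the final trauma recall

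*Combined protocol and SAP*

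**What the plan says.** Section 15 (Provisions to Protect Subjects) sets the only delayed distress check with a stated time: "participants will be contacted by the study coordinator within 24-72 hours of their writing session". Its stated purpose is to find raised distress in response to the writing.

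Trauma recall is not confined to writing. Section 10 lists a 5-minute recall block as the fourth part of the imaging protocol. Under Trauma Recall in fMRI it adds that "Two traumatic and two neutral conditions will be selected and played during scanning". It also states that "Participants will be scanned at baseline and after the 4 WED sessions writing about trauma in English or Spanish", and the same sentence includes the control group after its daily-activity writing. All three arms therefore have recall at Sessions 1 and 6.

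Section 9 (Study Timeline) places the repeat assessments about one month after writing ends, and then: "Upon completion of the session 6 participants involvement with the current study be complete and there will be no other study requirements".

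Section 14 provides that "participants will be queried regarding their distress levels before and after each session using the SUDS as well as the POMS", with immediate scoring. Section 15 adds a brief therapist check-in and a debrief after each recall. Section 17 names recall of severe trauma as the reason the study exceeds minimal risk.

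**The concern.** The sponsor evidently judged that same-day checks were not enough after writing, since it added a contact one to three days later. The in-scanner recall belongs to the class of exposure that Section 17 names as the main risk, and the women enter with raised PTSD symptoms (PCL-5 of 34 or above, Section 6). Yet the stated contact covers only the writing.

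The omission matters most at Session 6. After Session 1 a woman is still in the study: Section 16 describes weekly staff contact, and Table 1 schedules distress and mood ratings at the next session. After Session 6 nothing further is scheduled. If distress or suicidal thoughts emerge in the following days, the text states no step by which the team would ask. The 10-day reporting period in Section 14 starts only when the team becomes aware.

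What is at stake is participant safety. No endpoint, estimate or test depends on it.

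**Working it through.** No statistical figure in the plan needs to be reproduced. The check compares the safety provisions with the visit schedule, followed by simple arithmetic on size.

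**1. Does any provision supply a delayed check after Session 6?**

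- Coordinator contact at 24-72 hours (Section 15): delayed, but tied to writing in both trigger and purpose.
- Distress and mood ratings before and after each session (Section 14): same day.
- Therapist check-in of about 2 minutes (Section 15): after the writing or recall session, same day.
- Debrief after each recall (Section 15): no later time given.
- Heart rate, respiration and blood pressure monitoring and the squeeze ball (Section 15): during the scan.
- Post-scan surveys: Section 8 puts the battery after the scan, and Table 1 lists the Beck inventory at T6. Section 14 lets survey items start the suicide-risk steps. Same day.
- Exit interview (Section 8): same visit.
- Interview of women who complete the MRI (Sections 15 and 17): no timing and no distress purpose stated.
- Weekly staff contact (Section 16): for intervention problems that warrant withdrawal; not stated to continue after Session 6.

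None is stated as a delayed check after Session 6. The narrow reading of the contact sentence is fair. Elsewhere in Section 15 the before-and-after items are said to apply to writing or to trauma recall sessions, and the sentence on debriefing covers every recall. The contact sentence names writing alone.

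**2. Timing.** The last stated contact falls 1 to 3 days after the fourth writing session. Taking one month as 28 to 31 days (an assumption), it precedes the Session 6 recall by 28 − 3 = 25 to 31 − 1 = 30 days.

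**3. Size of the exposure.** Two traumatic scripts of 40 seconds each: 2 × 40 = 80 seconds if each is played once. One writing session lasts 30 minutes: 30 × 60 = 1,800 seconds. After the scan a woman stays on site for a task of about 30 minutes and a battery of 90 to 120 minutes: 30 + 90 = 120 to 30 + 120 = 150 minutes.

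**4. How many visits.** All 36 women are due a Session 6 scan, so at full attendance 36 visits lack a stated delayed contact. The documents give no rate of delayed distress after scanning. The one rate in Section 15, under 5% needing extra counseling, comes from trauma-writing trials and measures something else. Applied purely as illustration, 36 × 0.05 = 1.8, so fewer than 2 women.

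**5. Added workload.** Contacts already planned, if every woman is contacted after each of four writing sessions: 36 × 4 = 144. Adding Session 6: 36/144 = 25% more. Staff time at an assumed 5 to 15 minutes each: 36 × 5 = 180 minutes (3 hours) to 36 × 15 = 540 minutes (9 hours).

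**The case against.** The strongest reply is that the difference may be deliberate. Writing about trauma for 30 minutes on four occasions is a much larger exposure than about 80 seconds of script. Writing is described as online in Sections 8 and 9, while scans are attended on site with staff present for two hours or more afterwards. Session 6 also repeats a recall that each woman has already been through, and Section 15 excludes women at particular risk after recall. All of this stands, and it keeps the point modest. It does not remove it: the protocol never gives this rationale, Section 7 also mentions writing in a private office, and on-site care ends when she leaves.

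It is also fair to say that the closing sentence of Section 9 describes what is required of participants and does not bar staff from contacting them. The finding therefore rests on the absence of a stated contact.

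A reader might infer three stronger things, none of which the documents support:

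- That women are unprotected after the recall. The same-day measures are real and several.
- That delayed distress will not be looked for in practice. Sections 14 and 15 rely on distress and suicide-risk packets, and on procedures taken from an earlier study, that are not in the file.
- That control women receive no 24-72 hour contact at any point, because Section 8 uses the term writing probe in describing the trauma arms: "adopted along with a writing probe to assess the effect of WED". That phrase describes materials taken from earlier work. The contact sentence says participants without limit, and controls also have writing sessions.

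**Conclusion.** The point holds in a limited form. As written, the protocol states no delayed distress contact after the Session 6 scan visit for any of the 36 women, although that visit includes the final trauma recall and ends their involvement. Given the strong same-day cover and the short scripted exposure, this is a modest and inexpensive safety improvement. It is worth making, and it is no reason to question the design or the results.

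The conclusion rests on the text alone. It assumes that the unseen packets contain no such contact; if they do, the change only records it. The 80-second figure assumes each script is played once, and the count of 36 assumes full attendance.

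**What to change.** Reword the contact sentence in Section 15 so that the 24-72 hour coordinator contact follows each writing session and the Session 6 scan visit, and so that it asks about distress from either the writing or the trauma recall. Route any positive response to the suicide-risk and distress steps already in Section 14. The Session 1 scan visit may be added, though weekly contact and the Session 2 ratings partly cover it. A matching edit to the closing sentence of Section 9 is optional.

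The cost is a protocol amendment and 36 short contacts by the same coordinator, 3 to 9 hours in total under the assumption above. If Session 1 is included, this becomes 72 contacts (2 × 36) and 6 to 18 hours. No new staff, instrument or visit is needed. Contact with each woman would end up to 3 days after Session 6.
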